4.2.2 Analysis of Questionnaire Responses

We will provide descriptive summaries of the questionnaire answers to all vaccinations at Ti (before delivery of the intervention) and T6. No stratification into study arm will be implemented. Answers to questionnaire items containing free-text options will be categorized in either one of the provided answer options, if applicable, or as "other answer".

For questionnaire items expressed as Likert-type scales, we will assign integer scores to the responses ranging from 1 for "Disagree" to 5 for "Agree". We will provide a measure of internal consistency by means of Cronbach's alpha. The test-retest reliability will be assessed by calculating Pearson correlation coefficients between each GP's summated scores at Ti and T6, in each study arm separately.

For each GP, we will calculate an HPV knowledge score as the sum of all correct answers to the knowledge-related questions as well as an HPVv attitude score as the sum of all Likert-type answer scores to the attitude-related questions. We will use Wilcoxon signed-rank tests to assess for differences in HPV knowledge and HPVv attitude scores between Ti and T6.

4.2.3 Analysis of the Primary Objective

To analyze the primary objective, we will model the count of first administered HPVv doses at T6 using mixed-effect Poisson regression. The outcome variable will be the count of first HPVv doses administered by each GP at each of the time points T3 or T6. GP-level random intercepts will account for intra-GP correlation. The following fixed effects will define the grouping variables of the data set:

- Study arm (binary with levels control; active)
- Time point (binary with levels T3; T6)
- Baseline HPVv count (categorical with levels Never; Rarely (1–5 doses); Occasionally (6–10 doses); Regularly (at least 11 doses))
- GP gender (binary with levels male; female)
- GP age in years (continuous)
- GP workload (categorical with levels < 60%; 60–79%; 80–100%; based on the distribution of consultation counts according to workload in Swiss primary care (4))
- GP participation status in the cantonal HPVv program at inclusion (binary with levels yes; no)
- Patient gender (binary with levels male; female).

Each fixed effect other than the study arm will be included in the final model if a corresponding univariate analysis results in a *p*-value ≤ 0.2 .

The Poisson regression model will be assessed for overdispersion based on an asymptotic chi-squared test for the sum of squared residuals (5, 6). If the null hypothesis of no overdispersion is rejected at the 0.05 level, we will replace the Poisson model by a negative binomial model with the same fixed- and random-effect structure. A quasi-Poisson model will be considered as an alternative in case of an observed linear variance-to-mean relationship (7).

Rejection of the null hypothesis related to the primary objective (the effect associated with the study arm is equal to zero) will be based on the parameter estimate of study arm and its 95% confidence interval in the final model.

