2.8 Timing of Study Assessments

For each GP included into the study, we define the following timings:

- Baseline period Pb: A consecutive period of three months as recent as possible, but entirely before the intervention date Ti. Study participants will be asked to provide estimates of the number of HPVv doses administered during this period, which will be used for stratified randomization (see sections 2.2 and 3.3.1).
- Intervention date Ti: The day of delivery of the active and control intervention in the active intervention arm or of the control intervention in the control intervention arm. A questionnaire assessing knowledge on HPV and attitudes concerning HPVv will be administered at Ti, right before delivery of the intervention.
- Study start T0: The day of start of vaccination counting, usually scheduled on the 1st of the respective month following Ti. If Ti falls within the first week of a month, T0 is usually scheduled on the 15th of the same month.
- Follow-up at T3, T6, and T12: The dates at three, six and twelve months, respectively, after the study start T0. The questionnaire on HPV knowledge and HPVv attitudes will be delivered a second and final time at T6.
- **Study period**: The time interval between T0 and T6, which is the time interval relevant to the primary objective of the study.
- Follow-up period: The time interval between T6 and T12.
- Study end: The follow-up date T12, which indicates the end of all vaccination documentation.

3 Statistical Principles

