3.1 Confidence Intervals and *p*-Values

We will report statistical significance as determined in statistical null hypothesis tests by means of p-values. A level of significance of 0.05 will be used throughout the analyses. Accordingly, we will report two-sided 95% confidence intervals of coefficient estimates.

We will use a mixed-effects regression model for assessment of the primary objective and we will base rejection of the null hypothesis (no difference in effect on HPVv counts at T6 between the control and

intervention group related to the study hypothesis (see section 1.2) on statistical significance of a specific fixed effect coefficient estimate (see section 4.2.3).

Secondary outcomes will be assessed in an exploratory manner, and no adjustment for multiplicity will be implemented. We will judge resulting *p*-values with appropriate caution and consider the corresponding effect sizes.

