4.1 Objective Definitions

4.1.1 Primary Objectives

(1) To compare the first-dose HPVv counts at T6 between the intervention group and the control group.

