4.5 Statistical Software

Statistical analysis will be performed with the software R version 4.1.0 or higher (R Foundation for Statistical Computing, Vienna, Austria) (8).

5 Safety Analyses

This study will include no safety analyses, since no safety data collection will be required (2).

6 Reporting Conventions

For summary statistics, we will use one decimal place more than for the data from which they originate. We will make exceptions were deemed appropriate, such as for reporting of extremal values, where we will use the same number of decimal places as for the data from which they originate.

We will report quantities derived from regression models (coefficient estimates with confidence intervals and variance estimates) and values of test statistics up to three decimal places. We will report p-values of at least 0.001 up to three decimal places, and p-values smaller than 0.001 as "< 0.001".

7 Summary of Changes to the Protocol

The following points needed changes with respect to indications in the study protocol:

- Included GPs will not be asked for a precise number of administered vaccinations during Pb, but will provide a categorical estimate.
- Accordingly, the primary and secondary outcomes will not compare changes from T0 to the respective time points, but will assess the absolute HPVv uptake between T0 and the respective time points.
- Duration of Pb will be reduced from 6 months to 3 months due to practicability reasons.
- Accordingly, to ensure comparability with HPVv numbers during the baseline period, the measurements at 2 and 4 months after T0 will be replaced by one single measurement at 3 months after T0.

References

1. Grischott T. The Shiny Balancer – software and imbalance criteria for optimally balanced treatment allocation in small RCTs and cRCTs. BMC Med Res Methodol 2018; 18(1):108.

2. [name]. Impact of a multifaceted, targeted intervention on the HPV vaccination rate in Swiss Primary Care: A cluster randomized controlled study (Study protocol version 1.0). 2021.

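### The primary model pools nested T3 and T6 counts under one study-arm coefficient, which weights months 0–3 twice and equals the T0–T6 effect only if the arm rate ratio is constant

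*SAP*

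**What the plan says.** The target is stated consistently. Section 4.1.1 gives the primary objective as "To compare the first-dose HPVv counts at T6 between the intervention group and the control group". Section 3.1 gives the null hypothesis as "no difference in effect on HPVv counts at T6 between the control and" the intervention group. Section 2.8 defines the study period as "The time interval between T0 and T6, which is the time interval relevant to the primary objective of the study". Section 4.2.3 opens in the same sense: "we will model the count of first administered HPVv doses at T6 using mixed-effect Poisson regression".

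The next sentence of section 4.2.3 widens the outcome: "The outcome variable will be the count of first HPVv doses administered by each GP at each of the time points T3 or T6". Time point (T3 or T6) is listed as a fixed effect, to be kept only if it passes the univariate screen at p ≤ 0.2. No arm-by-time interaction is listed. Correlation within a GP is handled by a random intercept. The decision on the null "will be based on the parameter estimate of study arm and its 95% confidence interval in the final model".

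What a count at a time point covers is stated only in section 7, which says that the primary and secondary outcomes no longer compare changes "but will assess the absolute HPVv uptake between T0 and the respective time points". That clause describes what the SAP now does, not superseded protocol text.

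**The concern.** By the definition in section 7, the T3 count covers months 0–3 and the T6 count covers months 0–6. If both enter the model as rows, each first dose given in months 0–3 appears in both rows and each dose given in months 3–6 appears in one. With a single arm effect common to both rows, the tested coefficient is a blend of the T3 and T6 contrasts, not the T6 contrast.

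This matters when the effect changes over time, as it may after an educational session delivered on one day. The SAP nowhere assumes a constant effect, and it plans comparisons at T3, T6 and T12. None of the listed sensitivity analyses isolates T6: they change the population, add a practice-level intercept or impute missing data.

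**Working it through.** The SAP gives no figure for this model, so there is none to reproduce.

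**Step 1: what the arm coefficient uses.** For each GP let A be first doses in months 0–3 and B first doses in months 3–6. Given the GP's intercept, the rows are modelled as independent Poisson counts with a time effect and a common arm effect. The likelihood then factors into (i) a Poisson term for the GP's total over the rows and (ii) a term for how that total splits between rows, which does not involve arm. The arm coefficient therefore depends on the data only through the total:

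- planned rows (T0–T3 and T0–T6): A + (A+B) = 2A + B
- stated objective (T0–T6): A + B

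This does not depend on the number of GPs or the random-intercept variance. It also holds if rows are split further by patient gender, which section 4.2.3 lists as a fixed effect, or if time point is screened out. The negative binomial fallback keeps the same structure and still pools T3 and T6, but the 2:1 weighting is then no longer exact.

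**Step 2: size of the shift.** Let a and b be the control rates in the two windows, and RR1 and RR2 the arm rate ratios.

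- planned: (2a·RR1 + b·RR2)/(2a + b)
- T0–T6: (a·RR1 + b·RR2)/(a + b)
- difference: ab(RR1 − RR2)/[(2a + b)(a + b)]

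With a = b (an assumption) the difference is (RR1 − RR2)/6. The multiplier is not sensitive to that assumption. It is 2/(5×3) = 0.133 if the control rate is twice as high in the first window, and 2/(4×3) = 0.167 if it is twice as high in the second.

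| RR1 then RR2 | planned, (2·RR1+RR2)/3 | T0–T6, (RR1+RR2)/2 |
|---|---|---|
| 1.5, 1.5 | 1.50 | 1.50 |
| 1.6, 1.4 | 1.53 | 1.50 |
| 1.7, 1.3 | 1.57 | 1.50 |
| 2, 1 | 1.67 | 1.50 |
| 1, 2 | 1.33 | 1.50 |
| 1.5, 0.5 | 1.17 | 1.00 |

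**Step 3: rejection rates by simulation.** Assumed inputs: control mean of 3 first doses per window, random-intercept SD 0.8, 700 runs per setting. Section 2.4 gives 33 GPs without saying whether this is per arm or in total, so both 33 and 66 were run. Entries are median rate ratio and two-sided rejection at 5%.

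| GPs | RR1 then RR2 | planned | T6 only |
|---|---|---|---|
| 66 | 2, 1 | 1.68, 59% | 1.49, 44% |
| 66 | 1, 2 | 1.35, 26% | 1.51, 43% |
| 66 | 1.5, 1.5 | 1.55, 46% | 1.52, 48% |
| 66 | 1.5, 0.5 | 1.18, 10.7% | 1.01, 6.4% |
| 33 | 2, 1 | 1.67, 39% | 1.49, 29% |
| 33 | 1, 2 | 1.29, 16% | 1.42, 23% |
| 33 | 1.5, 1.5 | 1.49, 27% | 1.47, 28% |
| 33 | 1.5, 0.5 | 1.18, 9.9% | 1.00, 6.6% |

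The Monte Carlo standard error is about 2 percentage points for rates near 44%: √(0.44×0.56/700) = 0.019.

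With no effect in either window (1,000 runs per setting; 33 or 66 GPs, mean 1 or 3 doses, SD 0.01 or 0.8), the planned model rejected in 4.7–7.5% of runs and the T6-only model in 4.0–8.1%.

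**The case against.** **The rows may be meant as disjoint windows.** Section 4.2.3 does not say which months the T6 row covers. Section 7 also says that the 3-month measurement was chosen for comparability with the three-month baseline period, which would suit two 3-month windows. On that reading the total is A+B and nothing is counted twice. But section 7 says that the outcomes "will assess the absolute HPVv uptake between T0 and the respective time points", and if T6 meant months 3–6 only, an objective set at T6 would conflict with the T0–T6 period in section 2.8. No section states the disjoint reading, so the text needs correcting either way.

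**A time-specific contrast may be intended.** Section 4.2.4, item 2, speaks of the arm coefficient for the respective time points, so the missing interaction may be an omission. That is possible, but it does not change the decision rule in section 4.2.3, which names one arm estimate from a model with no interaction.

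**The consequence is conditional.** This stands. A reader might infer that the primary test addresses the wrong quantity whatever happens, or that counting early doses twice inflates the false-positive rate. Neither is supported. With a constant rate ratio the coefficient is the T6 effect, and with no effect in either window the random intercept absorbs most of the extra correlation. The excess rejection at equal T6 totals (10.7% against 6.4%) needs effects in opposite directions that cancel by T6. In the 2-then-1 and 1-then-2 settings a true T6 effect exists, so the differing rejection rates there are differences in power, not false positives.

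**The large figures come from extreme settings.** Also true: a doubling that vanishes entirely shifts the ratio by 0.17, whereas a change from 1.6 to 1.4 shifts it by 0.03.

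**Conclusion.** The point holds in a limited form. As written, the coefficient that decides the trial weights months 0–3 against months 3–6 by 2:1, whereas the stated objective weights them equally. The weighting follows from the Poisson random-intercept model and from section 7's definition of the counts, not from assumed rates. Its effect on the estimate depends on how far the arm rate ratio changes over the six months. Under equal control rates the shift is (RR1−RR2)/6, which is zero for a constant effect, about 0.03 for a mild decline and 0.17 for an effect that halves from 2 to 1. A fading effect is overstated at T6 and a growing one understated, with power altered accordingly. The simulated rates rest on the assumed dose means, intercept SD and GP numbers, and serve only to indicate direction and rough size.

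**What to change.** Either of two changes to section 4.2.3 brings the model into line with the objective:

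1. Use only the T0–T6 first-dose count in the primary model, with no T3 rows and no time-point term. Keep the GP random intercept and the planned overdispersion step. If patient gender is retained, there is one row per GP and patient gender. If it is screened out, there is one row per GP and the intercept itself takes up extra-Poisson variation, so the SAP should say how the overdispersion step then applies.
2. Keep two time rows, but define them as first doses in T0–T3 and in T3–T6. Their total is A+B, so the common arm coefficient targets T0–T6 uptake.

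In either case, state in section 4.2.3 which months each count covers, and analyse T3 and T12 in separate models as secondary objectives. Adding an arm-by-time term and reading the arm contrast at T6 would aim at the right quantity but leave the rows nested.

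The cost is SAP wording only. T3 is already a secondary time point, so no objective is lost and no new data are needed.

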2.2 Randomization

Randomization will occur cluster-wise on level of the practices where the enrolled GPs work. A statistician external to the study group will carry out stratified randomization into the active or control intervention group using the Shiny Balancer tool, which facilitates balanced allocation in cluster-randomised trials (1).

Stratification will occur according to the following factors:

- Participation status in the cantonal HPVv program at inclusion (yes/no).
- Estimated number of HPVv administered during the baseline period (4 categories, see section 3.3.1).

GPs enrolling in the trial when randomization of their practice has already taken place will be allocated to the corresponding study arm. GPs will need to be registered in the cantonal HPVv program before initiation of outcome measurements.

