4.2.5 Sensitivity Analyses

We will conduct all analyses described in sections 4.2.1 to 4.2.4 on the ITT population. Analyses of the primary and secondary study objectives will be repeated on the PPA population.

In addition, we will repeat analysis for the primary study objective by using a random-effect structure consisting of GP-level random intercepts nested within practice-level random intercepts to assess for clustering due to GPs working in the same practice.

Sensitivity analyses related to missing data are described in section 4.3.

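### Practices are randomised, but the model that decides the primary hypothesis has no practice level, so its 95% confidence interval is too narrow whenever GPs who share a practice have correlated counts.

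*SAP*

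**What the plan says.** - Unit of randomisation (SAP 2.2): "Randomization will occur cluster-wise on level of the practices where the enrolled GPs work".
- Shared practices (SAP 2.2): "GPs enrolling in the trial when randomization of their practice has already taken place will be allocated to the corresponding study arm". Two or more GPs can therefore belong to one practice and necessarily to one arm.
- Deciding model (SAP 4.2.3): a mixed Poisson regression of first-dose counts per GP at T3 and T6, in which "GP-level random intercepts will account for intra-GP correlation". No practice term is listed.
- Fallback under overdispersion (SAP 4.2.3): "we will replace the Poisson model by a negative binomial model with the same fixed- and random-effect structure". This adds no practice level either.
- Decision rule (SAP 4.2.3): rejection of the null hypothesis "will be based on the parameter estimate of study arm and its 95% confidence interval in the final model".
- Error level (SAP 3.1): "A level of significance of 0.05 will be used throughout the analyses. Accordingly, we will report two-sided 95% confidence intervals of coefficient estimates".
- Practice level (SAP 4.2.5): the primary analysis is repeated with "GP-level random intercepts nested within practice-level random intercepts to assess for clustering due to GPs working in the same practice". This repeat is listed under sensitivity analyses and covers the primary objective only.
- Secondary objectives (SAP 4.2.4): objectives 1 and 2 use models analogous to the primary one. Objectives 3 to 5 use logistic regression with no practice term.

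**The concern.** Study arm is constant within a practice. Any variation between practices that the covariates do not explain therefore enters the variance of the arm effect in full. A GP intercept deals with repeated rows from the same GP, such as T3 and T6. It does nothing for the correlation between two GPs who work in the same practice and were allocated together.

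At stake is the error rate of the one confirmatory test. If practice correlation is present and ignored, the interval that settles the primary hypothesis is too short, and a nominal 5% test rejects a true null hypothesis more often than that.

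**Working it through.** **Inputs from the SAP.** Practice as unit of randomisation (2.2); GP-only intercept in the deciding model (4.2.3); two-sided 5% level (3.1). The SAP does not give the number of practices, m or rho, so m and rho are varied below as assumptions.

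**The SAP's own figure.** SAP 2.4 gives 33 GPs with 30 patients each, 80% power, 9.5% against 14.9%, without saying whether 33 is the total or per arm. As a two-sided comparison of proportions without clustering, 33 in total (495 patients per arm) has 73.8% power and 33 per arm (990 per arm) has 95.7%. The stated 80% is reached at 33 per arm if patients within a GP have an intraclass correlation of about 0.025, which the SAP does not state. None of this gives a practice count or a practice correlation, so the figure cannot fix the size here. It only makes 66 GPs a possible reading for an illustration.

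**Formula.** Variance inflation DE = 1+(m-1)*rho. The correct interval is sqrt(DE) times as wide as the GP-only interval. True two-sided alpha = 2*(1-Phi(1.96/sqrt(DE))). Example, m=2 and rho=0.5: DE = 1.5, sqrt(DE) = 1.22, 1.96/1.225 = 1.60, alpha = 11.0%.

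| m | DE (rho 0.1 to 0.5) | Width factor | True alpha |
|---|---|---|---|
| 1 | 1.00 | 1.00 | 5.0% |
| 1.5 | 1.05 to 1.25 | 1.02 to 1.12 | 5.6% to 8.0% |
| 2 | 1.10 to 1.50 | 1.05 to 1.22 | 6.2% to 11.0% |
| 3 | 1.20 to 2.00 | 1.10 to 1.41 | 7.4% to 16.6% |

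**One illustrative scenario with unequal practices.** Assume 66 GPs in 30 practices of 1 to 4 GPs, a mean of 5 doses, and a between-GP log-variance of 0.7, half of it between practices. The size-weighted mean practice size is 178/66 = 2.70. The effective correlation is 0.35/(0.7+1/5) = 0.35/0.90 = 0.39. DE = 1+1.70*0.39 = 1.66 and alpha = 12.8%. In 350 simulated null trials the GP-only model rejected in 12.6-12.9%. The nested model rejected in 6.3% with a normal reference and 5.4% with a t reference on practices minus 2 degrees of freedom. With a quarter of the variance between practices the GP-only figure is about 9%; with 50 practices it is about 6-8%.

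**Separate simulation, GP-only Poisson model, no arm effect.** 600 trials per row; assumed mean parameter of 2 doses per period and between-GP log-variance 0.6. Here rho is the share of between-GP variance that lies between practices.

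| Practices x GPs | rho | Mean model SE | True SD of estimate | Rejection |
|---|---|---|---|---|
| 32 x 2 | 0 | 0.218 | 0.234 | 8.0% |
| 32 x 2 | 0.2 | 0.218 | 0.250 | 10.3% |
| 32 x 2 | 0.5 | 0.220 | 0.284 | 14.3% |
| 22 x 3 | 0.5 | 0.215 | 0.303 | 17.0% |

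The model's standard error does not respond to practice correlation, while the true spread grows. The 8.0% at rho = 0 is small-sample error of the Wald test, not clustering. At two GPs per practice the part due to clustering is therefore about 10.3-8.0 = 2.3 points (rho 0.2) and 14.3-8.0 = 6.3 points (rho 0.5). The formula gives 7.4-5.0 = 2.4 and 11.0-5.0 = 6.0.

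**Power.** If a design has 80% power with practice ignored, a correct analysis at m=2 has Phi(2.80/sqrt(DE)-1.96), which is 76% at rho 0.1 and 63% at rho 0.5.

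**The case against.** The strongest reply is that the harm is conditional. SAP 2.2 sets a rule for a GP who enrols late and SAP 4.2.5 acknowledges shared practices, but neither says how many practices will have more than one GP. If nearly all have one, the two models coincide. The randomisation is also stratified by programme status and baseline vaccination category. Both are candidate covariates and may absorb part of the practice variation, so a 50% residual share is at the high end. This stands as a limit on size. It does not remove the mismatch: the covariates other than arm enter only if a univariate p-value is at most 0.2, and residual correlation can remain.

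A second reply is that the nested model is already planned, and that SAP 4.2.4 allows models to be adapted after diagnostics. The first is true and makes the fix cheap, but a sensitivity analysis does not change which interval decides. The second is discretionary and names no practice term.

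Two stronger readings are tempting and not supported. A reader might infer that the type I error of this trial is known to exceed 5%, or is about 12.8%. The SAP gives no cluster sizes and no correlation, and part of any simulated excess can be small-sample Wald error. A reader might also infer that the plan leaves open which analysis counts if the two disagree. It does not: SAP 4.2.3 makes the GP-only final model decisive and SAP 4.2.5 makes the nested model supportive. The problem is that this order is the wrong way round.

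**Conclusion.** The primary test does not respect the unit of randomisation, and this should be corrected before analysis. That conclusion follows from the text of SAP 2.2, 4.2.3 and 4.2.5 alone. The direction of the error is clear if some practices hold two or more GPs and their counts remain positively correlated after adjustment. Its size cannot be fixed from the document: it runs from nil with one GP per practice to an interval that should be about 1.2 to 1.4 times as wide at two to three GPs per practice with rho 0.5.

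The secondary analyses are a lesser matter, since SAP 3.1 makes them exploratory. It would go too far to say that each of the logistic models has an uncorrected arm effect, because the covariates listed for objective 3 do not include study arm.

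**What to change.** - In SAP 4.2.3, make GP intercepts nested within practice intercepts the primary random-effect structure, and state that the negative binomial fallback carries the same structure. Move the GP-only model to SAP 4.2.5.
- State that the nested model is kept if the practice variance is estimated as zero; it then reduces to the GP-only model.
- Preferably, base the interval for the arm effect on a t reference with the number of practices minus 2 degrees of freedom.
- Objectives 1 and 2 then inherit the structure as analogous models. For the exploratory logistic models, use practice-clustered standard errors wherever study arm is a term.

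This is a change of wording, since both models are already specified. The cost is a somewhat wider interval and lower actual power if practices hold several GPs, and nearly none if most have one.

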2.1 Trial Design

2.1.1 Study Population

The study population will consist of GPs working in practices in German-speaking Switzerland. Fulfilment of all inclusion-exclusion criteria will be reviewed by the investigator or qualified designee to ensure that subjects qualify for the study.

Inclusion criteria:

- i) The GP works in the primary care setting.
- ii) The GP has been providing vaccinations according to the Swiss ministry of health (recommended basic and recommended additional vaccinations) for at least six months in their practice before study start. In detail: combined measles, mumps and rubella (MMR), meningococci, pneumococci, HPV, tick-borne encephalitis (TBE), chickenpox, shingles, and hepatitis A/B (combination and single vaccinations).

Exception: GPs not registered in the cantonal HPVv program can be included if they are willing to join the programme and have the eligible patient population in their practice to administer vaccinations.

Note: 'Providing vaccinations' means that a GP (or the practice they work at) in principle offers the vaccination to the patients. There is no need for a minimum number of vaccinated patients in the last six

months before inclusion into the study. For example, GPs registered in the cantonal HPVv program can be included even if they have not administered any HPVv doses during the previous six months.

Exclusion criteria:

- The GP predominantly provides pediatric care (reported by the GP as >50% of consultations).
- The GP predominantly provides gynecological care (reported by the GP as >50% of consultations).
- The GP is a school physician or provides vaccinations on behalf of schools.

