2.4 Sample Size

According to the study protocol (2), a sample size of 33 GPs, each recruiting 30 patients, will achieve a power of 80% at an alpha of 5% to detect a coverage change of +9.5% in the control group and of +14.9% in the active intervention group (according to a similar study (3))

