4.3 Missing Data

Missing data may potentially occur on two levels:

- GPs: baseline (including demographic) characteristics, failure to undergo the intervention, failure to return CRFs (including loss to follow-up) or questionnaires.
- Patients (data from the CRFs): demographic characteristics, type of vaccination.

To analyze the study objectives, we will use the following procedures to handle missingness in the ITT and PPA population data sets:

- Loss to follow-up of GPs: complete-case analysis.
- Missing baseline characteristics of GPs and missing patient-level characteristics: complete-case analysis.

For each study objective, we will conduct a sensitivity analysis on the IIT population using multilevel chained equations-based multiple imputation with 5 datasets and 20 iterations. We will restrict use of multiple imputation to this sensitivity analysis and use a complete-case approach for the main analysis due to the low anticipated drop-out rates (2).

For other analyses not belonging to a study objective, we will handle missing data by pairwise deletion (i.e., by omitting only cases with missing values of variables relevant to the current analysis).

The nature and frequency of missing data will be reported for all analyses. Differences in loss to followup frequencies between the study arms will be assessed using Pearson's chi-squared and Fisher's exact test.

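### The primary count is defined per GP, but the data set is grouped by patient gender with no rule for zero counts, so the arm estimate can depend on how the rows are built

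*SAP*

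**What the plan says.** SAP section 4.2.3 fixes the outcome: "The outcome variable will be the count of first HPVv doses administered by each GP at each of the time points T3 or T6". Random intercepts are at GP level. It continues "The following fixed effects will define the grouping variables of the data set", and the last item in that list is "Patient gender (binary with levels male; female", with the closing bracket following. Every fixed effect except study arm stays in the final model only if its univariate p-value is at most 0.2.

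Section 3.3.2 collects age and sex only for patients who receive one of the documented vaccines. Section 4.3 sets the missing-data rule: "Missing baseline characteristics of GPs and missing patient-level characteristics: complete-case analysis". Section 3.2 defines the ITT population as all randomised GPs.

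Zero counts are to be expected. Section 2.1.1 notes that "GPs registered in the cantonal HPVv program can be included even if they have not administered any HPVv doses during the previous six months", and section 3.3.1 has a Never category for baseline HPV doses. Section 4.2.4 reuses the primary model for secondary objectives 1 and 2, and section 4.2.6 refits it within each baseline category.

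**The concern.** A count per GP and time point has no patient gender. Once gender is a grouping variable, the row has to be a GP-by-time-by-gender cell. The two statements describe different data sets, and the outcome-driven screen then decides whether gender remains. If gender is screened out, the plan does not say whether the cells are added back together.

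Every other listed covariate belongs to the GP or the design and is defined whether or not a dose was given. Patient gender comes from the dose record. Someone who groups the dose records gets no row for an empty cell and none for a GP who gave no first dose. Someone who starts from the GP list gets zeros. The plan does not choose between them.

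The arm coefficient that decides the primary hypothesis is at stake. Moving a GP from no HPV vaccination to some is part of the effect sought, and it is the part that disappears if zeros are lost. The analogous models inherit the ambiguity, and the Never subgroup is the most exposed.

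**Working it through.** **Inputs.** Two-sided alpha of 0.05 (section 3.1). Illustrative rate ratio 14.9/9.5 = 1.568 (section 2.4), borrowed from coverage changes because the SAP gives no rate ratio. The SAP gives no expected first-dose count and no between-GP variance, so those below are assumptions shown over a range. There is no figure in the plan on this point to reproduce; the sample-size statement concerns proportions and does not bear on it.

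**Step 1: full grid with zeros entered.** For GP *i* at time *t*, let the two gender cells be Poisson with means λ and λ·e^δ, where log λ = α + β·arm + γ·time + u_i.

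- The total is Poisson with mean λ(1 + e^δ).
- Given the total, the split is binomial with probability e^δ/(1 + e^δ), which contains neither β nor u_i.

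The likelihood factorises, so β is estimated from the GP totals alone and is the same with or without gender. A numerical check (17 GPs per arm, random-intercept SD 0.8, means 1, 2 and 4, 20 data sets each) gave median differences in the log rate ratio of about 1e-8 and a largest of 0.003, attributable to numerical error. Exact equality need not hold for the negative binomial fallback.

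**Step 2: zero cells lost.** With control cell mean *a* and active mean *b* = 1.568*a*, the ratio of means among non-empty cells is

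[b/(1 − P0(b))] / [a/(1 − P0(a))].

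For Poisson, P0(a) = e^(−a). At a = 1: 1.568/(1 − 0.208) = 1.98 and 1/(1 − 0.368) = 1.58, a ratio of 1.25. For a negative binomial with k = 1, P0(a) = 1/(1 + a), so the ratio is (1 + b)/(1 + a); at a = 1 this is 2.568/2 = 1.28.

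| Control mean per cell | Poisson | Negative binomial, k = 1 |
|---|---|---|
| 0.25 | 1.07 | 1.11 |
| 0.5 | 1.14 | 1.19 |
| 1 | 1.25 | 1.28 |
| 2 | 1.42 | 1.38 |
| 3 | 1.50 | 1.43 |
| 5 | 1.56 | 1.47 |
| 10 | 1.57 | 1.52 |

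**Step 3: the mixed model itself.** Poisson random-intercept fits; 17 GPs per arm (reading the 33 GPs as a total, rounded up), SD 0.7, two time points, 40/60 gender split, 150 replicates, true ratio 1.57.

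| Control mean per GP per 3 months | All cells | Zero cells dropped | Only zero-dose GPs dropped |
|---|---|---|---|
| 1 | 1.68 | 1.19 | 1.42 |
| 3 | 1.55 | 1.31 | 1.50 |
| 6 | 1.47 | 1.38 | 1.46 |

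Rejection rates were 35%, 40% and 44% with all cells, and 5%, 31% and 40% with zero cells dropped, each uncertain by about 8 points. With a true ratio of 1 the all-cells fits rejected in 3%, 11% and 15% of runs, so these rates serve for comparison within a setting and not as power figures. Estimates under a true ratio of 1 stayed between 0.96 and 1.01 however the rows were built: losing zeros shrinks a real effect and does not create one.

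A second simulation (SD 0.8, one time point, 200 replicates, GP means 1, 2 and 4) gave medians of 1.55, 1.58 and 1.64 with zeros kept, and 1.15, 1.27 and 1.40 with empty cells dropped.

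**Step 4: blank sex.** A GP gives three first doses and leaves sex blank on one. Under the complete-case rule that GP's count becomes 2, although three doses are documented. The SAP gives no expected frequency of blank fields, so the size cannot be computed.

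**The case against.** A reader might infer that zero counts drop out as the plan is written and that the primary estimate is therefore biased towards no effect. The SAP does not support that.

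- No sentence drops zeros. Section 4.3 deals with fields missing for vaccinated patients; a patient who does not exist has no missing field.
- A GP who returns CRFs without an HPV dose has an observed count of 0. The CRFs cover several vaccines, so such a GP still has something to return.
- The ITT population is all randomised GPs, and the named models are ordinary, not zero-truncated, count models.
- Gender is a factor with two fixed levels, so an empty cell is well defined as 0.
- Gender splits the outcome rather than adjusting for a post-randomisation covariate. By step 1 it does no harm on a full Poisson grid.

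All of this stands, and it makes the attenuation conditional. It does not settle the matter: the unit is still stated in two incompatible ways, no sentence requires zeros to be entered, and the complete-case rule does reach a documented dose with blank sex. Section 4.2.4 allows ill-defined variables to be excluded, but that is discretion exercised after fitting, not a pre-specified rule.

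**Conclusion.** The plan contradicts itself on the unit of the primary model and leaves the handling of zero counts open. Two analysts following it could obtain different primary estimates. If the full grid is used, the Poisson arm estimate does not change. If rows are built from dose records, an illustrative true ratio of 1.57 falls to about 1.2 to 1.4 at low counts and changes almost not at all at Poisson cell means of 5 or more; with strong extra variation (k = 1) some shrinkage remains even there. These sizes rest on assumed dose rates and between-GP variation, and on the loss of zeros, which the plan permits but does not prescribe. Separately, the stated complete-case rule discards real first doses when sex is blank. The point merits a change to the text before analysis; it does not show that the primary result will be biased.

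**What to change.** In section 4.2.3, remove patient gender from the grouping variables and fixed effects, and so also from the analogous secondary and subgroup models. State that the data set has one row per GP and time point, built from the list of randomised GPs, with 0 entered where returned CRFs show no first HPV dose. GPs who return no CRFs remain missing under section 4.3 and are not zeros. Add to section 4.3 that a first dose with blank sex still counts.

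Report gender under secondary objective 6 or, if a model is wanted, in a supplementary one on the full GP-by-gender grid with explicit zeros.

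The cost is wording only; no new data are needed. The small downside is that the gender coefficient leaves the primary model.
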